### 7.4.2 DEVICE COMPLAINT REPORTING

Product complaints are any communication relative to the identity, quality, durability, reliability, safety, effectiveness, or performance of a device, or any report of a failure of a device to meet its performance. Entering a clinical study event into the database during this study will automatically result in an event that might be considered a product complaint associated with a BSC device being reported directly to BSC Consumer Affairs and any appropriate regulatory authority without any additional action required by the physician. If a reportable event is identified, BSC Consumer Affairs will seek to obtain as much of the following information as possible: name of the product, lot series number (if known), source of data/physician, event description, event start date, date of BSC notification, medical action taken, patient outcome (if known), investigation results, corrective action taken (if any), and regulatory reports (if any). These additional details for any device complaint will not be recorded in the Registry study database.

The Principal Physician will be responsible for reporting events to the IRB/EC based on local requirements. The Principal Physician will also be responsible for reporting any device complications that occur after the time of study exit and all updates to device complications that are unresolved at the time of study exit using the usual process applicable to market-released devices.

### 7.4.3 SAFETY REPORTING

#### **Definitions and Classification**

Adverse event definitions are provided in Table 2. Administrative edits were made to combine definitions from ISO 14155-2011 and MEDDEV 2.7/3 (2015).

 Table 2: Safety Definitions

Table 2: Safety Definition	
Term	Definition
Adverse Event (AE) Ref: ISO 14155-2011	Any untoward medical occurrence, unintended disease or injury, or any untoward clinical signs (including an abnormal laboratory finding) in subjects, users or other persons, whether or not related to the investigational medical device.
Ref: MEDDEV 2.7/3 (2015)	
Serious Adverse Device Effect (SADE)	Adverse event that: a. Led to death, b. Led to serious deterioration in the health of the
Ref: ISO 14155-2011	subject, that either resulted in as defined by either: 1.a life-threatening illness or injury, or
Ref: MEDDEV 2.7/3 (2015)	2.a permanent impairment of a body structure or a body function, or
	
 
3.in-patient or prolonged hospitalization, or
 
4.medical or surgical intervention to prevent life-threatening illness or injury or permanent impairment to a body structure or a body function,
 

	c. Led to fetal distress, distress death or a congenital abnormality or birth defect.
	NOTE: Planned hospitalization for a pre-existing condition, or a procedure required by the Clinical Investigational Plan, without serious deterioration in health, is not considered a serious adverse event.
Unanticipated Adverse Device Effect (UADE)	Any serious adverse effect on health or safety or any life- threatening problem or death caused by, or associated with, a device, if that effect, problem, or death was not previously
Ref: 21 CFR Part 812	identified in nature, severity, or degree of incidence in the investigational plan or application (including a supplementary plan or application), or any other
	unanticipated serious problem associated with a device that relates to the rights, safety, or welfare of subjects.
Unanticipated Serious Adverse Device Effect (USADE)	Serious adverse device effect which by its nature, incidence, severity, or outcome has not been identified in the current version of the risk analysis report.
Ref: ISO 14155-2011	NOTE 1 : Anticipated serious adverse device effect (ASADE)
Ref: MEDDEV 2.7/3 (2015)	is an effect which by its nature, incidence, severity or outcome has been identified in the risk analysis report.

Table 2. Galety Deminitions		
Term	Definition	
Device Deficiency	An inadequacy of an investigational medical device related to its identity, quality, durability, reliability, safety or	
Ref: ISO 14155-2011	performance. This may include malfunctions, use error, or inadequacy in the information supplied by the manufacturer.	
Ref: MEDDEV 2.7/3 (2015)		

 Table 2: Safety Definitions

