#### Endpoint:

- Complications (adverse device effects/events)
  - Intra-operative device or surgery related complications reported during Implantation visit (e.g., cylinder crossover)

- Post-operative device or surgery related complications reported during follow-up (e.g., mechanical malfunction, infection)
- Unanticipated and serious adverse device effects (per ISO 14155:2011)
- Deaths (related to the device or implantation procedure)
- Device Malfunctions
  - Device deficiencies or malfunctions (per ISO 14155:2011)
- Revision procedures related to the device or implantation procedure

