## 16.1 PHYSICIAN REPORTS

Physician is responsible for preparation and submission of the following reports as identified in Table 5 below.

Report	Submit to	Description
Clinical Study Events	Sponsor/IRB/EC	Unanticipated adverse device Effect (UADE), and Serious Adverse Device Effect (SADE) need to be submitted to the Sponsor and may need to be submitted to the IRB/EC in accordance with the IRB/EC requirements at the study site, as soon as possible but no later than 10 working days after the physician learns of the event
Study Patient Death	Sponsor/IRB/EC	Death must be reported to the sponsor and may need to be submitted to the IRB/EC in accordance with local requirements, no later than 10 working days after the physician learns of the death
Withdrawal of IRB/EC approval	Sponsor	The physician must report a withdrawal of approval by the reviewing EC/ IRB of the physician's part of the study, within 5 working days of the physician learning of the withdrawal of approval
Progress Report	Sponsor/IRB/EC	The physician must submit this report to the sponsor and the IRB/EC at regular intervals in accordance with the IRB/ EC requirements at

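### Table 2 defines Serious Adverse Device Effect without requiring any link to the device or the procedure

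*Combined protocol and SAP*

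**What the plan says.** Section 7.4.3 is where the protocol places its safety definitions, and it states that they were combined from two source standards.

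- **Adverse event row, Table 2:** covers untoward occurrences "whether or not related to the investigational medical device".
- **SADE row, Table 2:** opens with "Adverse event that: a. Led to death" and goes on to serious deterioration in health, followed by the forms that deterioration can take. One of these is "in-patient or prolonged hospitalization, or" a further listed alternative. Fetal and congenital outcomes complete the row. No limb mentions the device or the procedure.
- **NOTE inside the SADE row:** certain planned admissions, if "without serious deterioration in health, is not considered a serious adverse event". Table 2 has no row for serious adverse event.
- **Other rows, Table 2:** the unanticipated adverse device effect (UADE) row does require causation by, or association with, a device. The USADE row adds only unexpectedness to SADE. There is no row for adverse device effect, although Sections 7.4.1 and 8.2 use the term.
- **Tables 3 and 4:** the investigator must assess each adverse event's relationship to the device and to the procedure. The SADE row does not refer to either assessment.
- **Section 8.2, endpoints:** "Unanticipated and serious adverse device effects (per ISO 14155:2011") is listed, and so is "Deaths (related to the device or implantation procedure").
- **Section 16.1, Table 5:** "Serious Adverse Device Effect (SADE) need to be submitted to the Sponsor" no later than 10 working days after the physician learns of the event.

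**The concern.** The SADE row reads as a serious adverse event definition placed under a device-effect heading. Its own NOTE uses the serious adverse event term, and the neighbouring UADE row shows that the table includes a device link where one is meant.

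Two things depend on the term: a safety endpoint and a timed reporting duty. A site that follows Table 2 literally would classify a serious event as a SADE whatever its cause. A site that follows Section 7.4.1 would confine itself to related events. The SADE and USADE counts could then depend partly on which section a site had read, with up to 16 sites taking part.

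**Working it through.** The plan states no figure on this point, so the check is to carry two test events through each provision. Both are assumed to be judged Unrelated under Table 3 and also unrelated to the procedure under Table 4.

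| Provision | Unrelated death | Unrelated, unplanned admission with serious deterioration |
|---|---|---|
| Table 2, adverse event | Met | Met |
| Table 2, SADE | Met, criterion a | Met, criterion b (hospitalization limb) |
| Table 2, USADE | Met if not identified in the risk analysis report | Same |
| Table 2, UADE | Not met: device link required | Not met |
| Section 7.4.1, recording of related complications | Outside | Outside |
| Section 7.4.1, sentence on the purpose of the event form | Inside: it covers any event during or after implantation | Inside |
| Section 8.2, opening sentence | Outside: device or surgery related events only | Outside |
| Section 8.2, SADE bullet | Inside by Table 2, outside by the opening sentence | Same |
| Section 8.2, death bullet | Outside | Not applicable |
| Table 5, SADE duty | Reportable by Table 2 | Reportable by Table 2 |
| Table 5, death duty | Reportable whatever the cause | Not applicable |

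Three results follow.

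1. An event judged Unrelated satisfies every element of the SADE definition. The relatedness assessment exists but does not enter the classification.
2. The same unrelated death is a SADE under Table 2 and is not an endpoint death under Section 8.2.
3. Whether an unrelated event enters the SADE endpoint depends on whether Table 2 or the opening sentence of Section 8.2 governs. The plan does not say.

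**Size.** Let r be the rate of related serious events, u the rate of unrelated ones, and c the share of unrelated ones that are captured and labelled SADE. If no man has both kinds, the count is inflated by (r + c·u)/r = 1 + c·u/r. The sample size cancels. The documents give none of r, u or c, so no value can be computed.

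What can be shown is the weight of a single event in the planned by-device summaries. Using the one-year implant numbers in Section 8.1 as denominators, one misclassified event moves the proportion by 1/500 = 0.2 percentage points for AMS 700, 1/20 = 5 points for Spectra and 1/15 = 6.7 points for Ambicor. This is the leverage of one event and not an estimate of how many there will be.

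**The case against.** The strongest reply is that each use of SADE meets a relatedness condition somewhere else. The duty in Table 5 sits in the row for clinical study events, which Section 7.4.1 describes in terms of complications, malfunctions and related revisions. Section 8.2 opens by limiting the safety assessment to device or surgery related events, and its SADE bullet falls under that sentence. The standard follow-up question asks about penile surgery or trouble with the device and would not bring out most unrelated admissions. An unrelated event reported in error should carry an Unrelated assessment, so it could be separated later. All deaths go to the sponsor within 10 working days under their own row in Table 5, so an unrelated death is reported on the same clock in any case.

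Most of this stands as a limit on the consequence. It does not repair the definition. Sections 7.4.1 and 8.2 conflict with Table 2 without amending it, and the sentence in Section 7.4.1 on the event form is itself broader than related events. The endpoint bullet cites an ISO standard, but Table 2 credits the same standard for its SADE row, so within the documents the citation settles nothing.

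A reader might go further and infer that unrelated deaths and hospital stays in general will be counted as device effects, and that the SADE count will be inflated several-fold. The documents do not support that:

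- The collection rules probably keep many unrelated events out of the database.
- The hospitalization limb applies only where health has seriously deteriorated, and the NOTE removes some planned admissions.
- Any multiple would merely restate assumed rates that appear nowhere in the plan.

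All-cause death reporting alongside a related-death endpoint is also not a contradiction in itself. The contradiction lies in the SADE label.

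**Conclusion.** The SADE definition is wrong as written, with minor severity. Read literally, it classes a serious event assessed as Unrelated as a device effect, and USADE inherits this. That conflicts with the related-events scope of Sections 7.4.1 and 8.2 and with the related-deaths endpoint.

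The effect is confined to SADE and USADE classification, the SADE endpoint count and SADE reporting. Nothing in the plan ties the Kaplan-Meier analysis of major complications to SADE. The intra-operative and post-operative complication, malfunction and revision endpoints stand separately. No hypothesis test, stopping rule or sample size uses the SADE count.

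The size of any miscount cannot be estimated from the documents, and no fold-increase should be stated. The conclusion rests only on the wording of Table 2 set against the other sections, with no assumption about event rates.

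**What to change.** 1. Add an adverse device effect row to Table 2: an adverse event assessed as related to the device (Table 3) or to the implantation procedure (Table 4).
2. Redefine SADE as an adverse device effect that meets the existing seriousness criteria. USADE is then corrected automatically.
3. If all-cause serious events are wanted, keep the present text and its NOTE under a separate serious adverse event row.
4. State in Section 8.2 that the SADE endpoint is tabulated using the investigator's relatedness assessment, with the same rule for the death endpoint.

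Two details need settling at the same time. The sentence introducing Table 4 names three relationship categories while the table has two, so the rule must say which count as related. The items that Section 7.4.1 lists for recording do not include relatedness, so the sponsor should confirm that the event form carries it.

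The cost is protocol wording and a site memo. The plan already requires the assessments, so no new patient contact is needed.

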#### Relationship to Study Device(s)

The investigator must assess the relationship of the AE to the study device as related or unrelated. See criteria in Table 3:

Classification	Description
Unrelated	• The adverse event is determined to be due to a concurrent illness or effect of another device/drug and is not related to the investigational product.
Related	
 
The adverse event is determined to be potentially related to the investigational product, and an alternative etiology is equally or less likely compared to the potential relationship to investigational product, or
 
There is a strong relationship to investigational product, or recurs on re-challenge, and another etiology is unlikely, or
 
There is no other reasonable medical explanation for the event.
 

Tab	le 3:	Criteria f	for As	sessing	Relationship of Study	/ Device to Adverse Event
			1			

#### Relationship to Study Procedure

The investigator must assess the relationship of the AE to the study procedure as unrelated, possibly related, or probably related. See criteria in Table 4:

### Table 4: Criteria for Assessing Relationship to Study Procedure

Classification	Description			
Unrelated	
 
No evidence that the timing of the adverse event has a
 
			
	relationship to the procedure performed.			
Related	
 
The adverse event has a timely relationship to procedure performed.
 
			
	However, a potential alternative etiology may be responsible for the adverse event.			

# 8 STATISTICAL METHODS AND DATA ANALYSIS

Analyses of multi-center data for initial publication(s) may be performed after approximately 500 patients complete 1 year follow-up. Additional individual and multicenter data analyses may be performed as warranted throughout the study for publication(s). Analysis for study publications is planned after the study enrollment is complete and all the enrolled patients have completed their 1-year and 5-year follow-up evaluations.

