# 5 PATIENT ELIGIBILITY

The PROPPER Registry is expected to enroll approximately 500 to 1500 patients at up to 16 sites throughout the US and Canada. Enrollment is expected to be over a one to two year period with up to five year patient follow-up.

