# 8.1 SAMPLE SIZE

Up to 1500 patients with erectile dysfunction (ED) electing to receive a BSC penile prosthesis implant will be included in this registry over a 1- to 2-year enrollment period. A total of more than 500 patients are anticipated to be implanted and entered into the registry database per year of enrollment, based on the following BSC historical estimates of the number of each BSC penile prosthesis type implanted, and assuming 10 to 15 participating physicians:

- 500 AMS 700®
- 15 AMS Ambicor®
- 20 Spectra™

The minimum sample size for multi-center data analysis will depend on the total number of patients, or the number of patients with each type of penile prosthesis implanted for whom sufficient follow-up data on multiple endpoints of interest are available. Generally, a minimum follow-up of at least one year after implantation is desired for analysis of data for the device subsets with previous clinical outcomes reported in the literature (e.g., AMS 700®, AMS Ambicor®). Because clinical data has been published from multiple studies including more than 100 patients implanted with AMS 700® devices in the past decade (since the introduction of the InhibiZone antibioticimpregnated devices and the current MS Pump), analysis of less than 100 patients implanted with these devices with at least one1 year of follow-up is not planned. However, an analysis sample size as small as 10 to 25 patients implanted with the newer Spectra™ or AMS 700® Series devices with the Conceal Low Profile reservoir, with 6 to 12 months of post-implant follow-up, may be of value for publication in the scientific literature due to the lack of any prospective clinical outcomes published to date for these products.

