#### Statistical Analysis:

Descriptive statistics (number of events, number and proportion of patients) will be summarized by complication category by device type and for the full group. Kaplan-Meier method will be used to estimate the major complication event rate at 1 year postoperative follow up by device type and overall for all BSC penile prostheses recipients.

Descriptions will also be prepared of the following details associated with device related complications in each category, and will include the following as available for each:

- Treatment for complication
- Location of treatment
- Resolution (resolved or continuing)

Additional analyses may be prepared for other follow-up time such as 6 month, 2, 3, 4, and 5 years.

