#### Determination of Patients for Analysis:

All enrolled patients that received a BSC penile prosthesis with data available will be included.

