#### 8.3 EFFECTIVENESS OBJECTIVES

Effectiveness of the BSC penile prostheses will be assessed in all patients with data available at the required 1-year ( $\pm$  4 months) post-operative follow-up, and any of the following additional follow-up time points with data available:

- 3 months (± 1 month)
- 6 months (± 1 month)
- 18 months (± 1 month)
- 2 years (± 4 months)
- 3 years (± 6 months)
- 4 years (± 6 months)
- 5 years(± 6 months)

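### At the initial analysis the complication-category proportions may mix follow-up from days to almost 2 years, so they cannot be read as 1-year risks

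*Combined protocol and SAP*

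**What the plan says.** Section 8, repeated in the synopsis, sets a permissive trigger: "Analyses of multi-center data for initial publication(s) may be performed after approximately 500 patients complete 1 year follow-up". Further analyses are planned once all men have completed their 1-year and 5-year evaluations.

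For safety, section 8.2 defines the analysis set as follows: "All enrolled patients that received a BSC penile prosthesis with data available will be included". Procedure details are required data (Table 1, section 7), so on its wording a man implanted shortly before the analysis belongs to the set. The main summary is then: "Descriptive statistics (number of events, number and proportion of patients) will be summarized by complication category by device type and for the full group". No period is given for the events, and no minimum follow-up for the men.

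The same section plans one estimate tied to a time point: the Kaplan-Meier "method will be used to estimate the major complication event rate at 1 year postoperative follow up by device type and overall". It covers major complications, a term section 8 does not define. Estimates at other times are optional.

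On pace, section 8.1 states: "A total of more than 500 patients are anticipated to be implanted and entered into the registry database per year of enrollment". Section 5 adds: "Enrollment is expected to be over a one to two year period with up to five year patient follow-up", with about 500 to 1500 men in total.

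**The concern.** The trigger counts men who have completed a year, while the denominator counts men who have been implanted. Nothing in the plan links the two. When enrolment is long relative to the trigger, the first table can hold about as many men with less than a year of follow-up as men with a full year. A proportion over such a mixture estimates no defined risk: it depends on how fast men were enrolled and on the date the data were cut.

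Safety and durability are among the registry's main objectives (section 3.1). Section 2.2 states an aim of comparison with historical results, although only for the effectiveness measures. Readers of the first publication are likely to set its complication proportions beside published series, and without a common follow-up time that comparison is not sound.

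**Working it through.** **Inputs from the documents.** Trigger: 500 men with 1 year completed (section 8). Annual implants by device: 500 AMS 700, 15 Ambicor, 20 Spectra (section 8.1). Enrolment of 1 to 2 years and 500 to 1500 men (section 5).

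**Assumptions not in the documents.** Uniform accrual, 1-year evaluations completed at 12 months, a 10% 1-year risk for a complication category, and the hazard shape.

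**Reproducing the accrual figure.** 500 + 15 + 20 = 535 per year, consistent with the stated more than 500.

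**Share of men under 1 year.** Let r be accrual per year, E the enrolment period in years, and c the fraction completing the 1-year evaluation.
- Trigger time T = 1 + 500/(r·c).
- Implanted by T = r·min(T, E).
- Implanted at least 1 year earlier = 500/c.

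Base case (r = 535, E = 2, c = 1): T = 1 + 500/535 = 1.93 years; implanted 535 × 1.935 = 1,035; under 1 year 1,035 − 500 = 535, or 51.7%.

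| Scenario (c = 1) | T (years) | Implanted | Under 1 year | Share |
|---|---|---|---|---|
| 500 men in total, enrolled in 1 year | 2.00 | 500 | 0 | 0% |
| 535/year, 1 year | 1.93 | 535 | 35 | 6.5% |
| 535/year, 1.5 years | 1.93 | 802 | 302 | 37.7% |
| 535/year, 2 years | 1.93 | 1,035 | 535 | 51.7% |
| 1,500 men over 2 years (750/year) | 1.67 | 1,250 | 750 | 60% |
| 1,500 men in 1 year | 1.33 | 1,500 | 1,000 | 66.7% |

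Incomplete 1-year contact delays the trigger. In the 535/year, 2-year case, c = 0.8 gives T = 2.17, 1,070 implanted, 1,070 − 625 = 445 under 1 year (41.6%). With c = 0.7 the share is 33.2%.

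**Effect on a crude proportion.** Take F(t) = 1 − exp(−λt) with F(1) = 10%, so λ = −ln 0.9 = 0.1054.
- Base case, first-year events only. The 500 older men contribute 500 × 0.10 = 50 events. The 535 younger men have mean risk 1 − 0.10/0.1054 = 0.0509, giving 27.2 events. Crude proportion: 77.2/1,035 = 7.5%.
- Base case, all events. Follow-up is uniform from 0 to 1.935 years, so the proportion is 1 − [1 − exp(−0.2038)]/0.2038 = 9.5%.
- 1-year enrolment, all events. Follow-up is uniform from 0.935 to 1.935 years: 1 − [exp(−0.0985) − exp(−0.2038)]/0.1054 = 1 − (0.9062 − 0.8156)/0.1054 = 14.0%.

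With a front-loaded hazard (Weibull, shape 0.5) the three figures are 8.3%, 9.3% and 11.8%. Assumed risks of 5% and 20% give similar relative errors.

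**After the change.** Restricting the crude proportion to the 500 men with a year of potential follow-up and to first-year events returns 10%. A Kaplan-Meier estimate at 1 year also targets 10%, provided censoring is unrelated to risk and events are captured.

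**The case against.** The plan permits this problem; it does not require it. Section 8 says the early analysis may be done, and section 18 describes aggregate publication for all enrolled men after 1-year follow-up. Section 8.1 states a general preference for at least a year of follow-up for AMS 700 and Ambicor, which are 515 of the 535 men expected per year (96%). The only safety figure the plan labels as a 1-year rate is the Kaplan-Meier estimate, which handles short follow-up. All of this is fair. But the preference in section 8.1 is not carried into the safety set, and the same section contemplates analysing Spectra or Conceal-reservoir men with 6 to 12 months of follow-up. The Kaplan-Meier estimate leaves every category not classed as major uncorrected.

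A reader might also infer three stronger things that the documents do not support.

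- *The proportions will come out too low.* That follows only if events are cut at 12 months, which section 8.2 does not do. Counting all events gives about 9.5% in the base case and about 14% with 1-year enrolment.
- *The proportions could be about half the true risk.* That would need no event to be known before the 1-year contact (50/1,035 = 4.8%). Table 1 requires events, where applicable, at the procedure and at interim follow-up as well. Intra-operative complications are recorded at surgery and are not diluted at all.
- *The 1-year effectiveness tables are biased too.* Section 8.3 allows a window of ± 4 months, and nothing in the documents suggests that men seen early in it answer differently from men seen late.

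**Conclusion.** The point holds as a gap in definition. At the initial analysis the crude category proportions have no fixed follow-up, event window or cut-off, so they cannot be read as 1-year risks. How much this matters depends on enrolment: it is negligible if enrolment stops at about 1 year and only first-year events are counted, and substantial if enrolment runs to 2 years. The 52% share rests on 535 men per year, a 2-year enrolment and full 1-year completion. The upper end of the range, 67%, needs 1,500 men in a single year, well above the device estimates in section 8.1. The 7.5%, 9.5% and 14% figures rest on an assumed 10% risk and constant hazard; they show that the error can go either way and do not predict its size. Major complications are covered by the planned Kaplan-Meier estimate. The final analysis, after all men reach their follow-up, is not affected by staggered entry. This is a cheap improvement to the plan for the first publication and does not undermine the registry as a whole.

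**What to change.** In sections 8 and 8.2 and in the synopsis:

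1. State a data cut-off date for the initial multi-center analysis.
2. Extend the planned 1-year Kaplan-Meier estimate (or a cumulative incidence estimate) to every complication category and to revision procedures, by device type and overall, with men censored at last contact.
3. Limit any crude 1-year proportion to events in the first 12 months among men implanted at least 12 months before the cut-off, and show how many of those men have had the 1-year contact. That count matters: if, as an extreme, events surfaced only at that contact and 80% of men were reached, a true 10% would still read as 0.8 × 10% = 8%.

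The cost is a few more tables and a smaller denominator for the crude proportions in the first publication (500 instead of 1,035 in the base case). The date of procedure is already required, so no new data or patients are needed.
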